## 9.2. SERIOUS ADVERSE EVENTS

### 9.2.1. Definition of a Serious Adverse Event

An adverse event or suspected adverse reaction is considered 'serious' if, in the view of the investigator, it results in any of the following outcomes:

- (a) Death;
- (b) Is life threatening;
- (c) Results in persistent or significant incapacity or substantial disruption of the ability to conduct normal life functions;
- (d) A congenital anomaly/birth defect;
- (e) Requires in-patient hospitalization or prolongs an existing hospitalization;
- (f) An important medical event that may jeopardize the patient or subject and may require medical or surgical intervention to prevent one of the outcomes listed above.

### 9.2.2. Reporting SAEs

In agreeing to the provisions of this protocol, the investigator accepts all legal responsibilities for immediate reporting of SAEs to the study designated physician ([name] or his designee) as described below.

**Table 4: Requirements for Reporting AEs to various stakeholders**

	Local IRB	NIAAA	DSMB	Other centers	Intercept	FDA
AEs	Continuing Review	Annual Report	Every 6 months	DSMB reports (every 6 months)	DSMB reports (every 6 months)	Annual Report
TEAEs	Continuing Review	Annual Report	Every 6 months	DSMB reports (every 6 months)	DSMB reports (every 6 months)	Annual Report
SAEs	Continuing Review	2 working days	Every 6 months	DSMB reports (every 6 months)	DSMB reports (every 6 months)	Annual Report
SUSAR	5 days	2 working days	2 working days	2 working days	2 working days	7 days if death 15 days if other
Fatality	If unrelated Follow SAE timeline If related follow SUSAR timeline					

AE: Adverse Event; TEACs: Treatment Emergent Adverse Event; SAE: Serious Adverse Event; SUSAR: Serious Unsuspected Adverse Reaction; DSMB: Data and Safety Monitoring Board

The study designated physician for TREAT 002 is [name].

Safety Officer for the DCU of the TREAT Consortium is [name].

All SAEs must be reported to the DCU (i.e., within 2 working days) after the investigator identifies the SAE. SAEs should be entered into the OnCore system within 2 working days of the investigator becoming aware of the event. An initial report by telephone should be followed as soon as possible by completion of the SAE CRF. Any supporting source documentation should be emailed to the assigned contact information as soon as possible. At a minimum the following information should be provided at the time of the initial report: 5-digit Study ID, a description of the event, at least one criterion classifying the event as Serious and the name and title of the reporting individual. Additionally, judgment of causality by the investigator must be provided as soon as possible to ensure timely reporting to regulatory authorities.

Following the initial report, any additional information obtained by the investigator about the SAE must be reported promptly to the DCU.

The site investigator will assess whether the event is causally related to the study medication. The study designated physician ([name]) will consider the investigator's assessment, however, since he holds the IND and is primarily responsible for the overall safety of the participants, his causality assessment will take precedence over that of the site investigator. The study designated physician will determine if an SAE meets the criteria for an IND safety report (*suspected, unexpected serious adverse reaction* (SUSAR) in accordance with the FDA regulations, 312.32(c)(1)(i).

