## **5.5 UNBLINDING PROCEDURES**

### **5.5.1 Unscheduled, Emergency Unblinding**

The site pharmacist will be unblinded to randomization codes and corresponding treatment assignment as s/he will overlabel each bottle to apply the blind, prior to dispensing to any subjects at the site. Additionally, the randomization codes and corresponding treatment assignment will be maintained by the TREAT DCU. The study designated physician ([name] or his designee), or the individual investigators will not have access to this information. In the event that a medical emergency necessitates unblinding (i.e., in situations where knowledge of the blinded treatment is necessary for further medical management of the patient), the site investigator (or his/her designee) will contact the designated study physician to discuss the rationale for unblinding. If there is a difference of opinion between the designated study physician and the site investigator, then the site investigator retains the final right to seek unblinding. The designated study physician will

communicate with the DCU about the decision to unblind the subject and then the DCU will unblind the subject by interacting directly with the site investigator.

The Data and Safety Monitoring Committee (DSMC) will be able to unblind patients. Cases of premature unblinding (as noted above) will be reviewed by the DSMC.

Access to randomization codes and corresponding treatment assignment will also be made available to the designated study physician who is responsible for reporting SAEs and suspected unexpected serious adverse reactions (SUSARs) to the Regulatory Authorities and should be accessed only in the event that reporting necessitates unblinding. Aside from the site pharmacist who conducts the drug overlabeling, no other site personnel will have direct access to blinded patient treatment codes until all trial data have been entered onto the trial database and validated, and the database locked.

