## **5.9 TRIAL OR SITE TERMINATION**

The TREAT consortium reserves the right to terminate the trial at any time. It is normal procedure to review the emerging clinical and safety data. As a result of such a review or a recommendation by the DSMC, it may be necessary to stop the trial before all patients have completed the trial.

It is the responsibility of the individual site's PI to report to their Institutional Review Board (IRB) of discontinuation of the trial and the reason for doing so in a timely fashion according to institutional policies.

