### **8.5. OTHER SAFETY RELATED CLINICAL OUTCOMES**

The following clinical outcomes will be assessed:

- Death (from hepatic and non-hepatic related causes)
- Complications of portal hypertension including gastroesophageal bleeding, interventions to manage variceal bleeding (e.g., variceal banding/sclerotherapy or TIPS placement) and diuretic resistant ascites
- Complications of Cirrhosis: new-onset ascites, hepatic encephalopathy, hepatorenal syndrome (type I or II), and spontaneous bacterial peritonitis).
- Hospitalization

Each of these events including hospitalizations will be adjudicated by the site

investigator as expected as part of the natural history of moderately severe AH, or unexpected (e.g., suicide, motor vehicle accident, or myocardial infarction).

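### Table 4 sends a death judged unrelated to the safety committee only on the 6-monthly schedule, while the NIAAA and the DCU get it within 2 working days; all deaths should go to the committee chair on that shorter clock

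*Combined protocol and SAP*

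**What the plan says.** Table 4 in section 9.2.2 sets the reporting clocks. Its Fatality row creates no clock of its own but points to two other rows: "If unrelated Follow SAE timeline If related follow SUSAR timeline". The SAE row gives the NIAAA 2 working days, the DSMB every 6 months, other centers and the drug supplier the 6-monthly DSMB reports, the FDA the annual report and the local IRB continuing review. The SUSAR row gives the DSMB 2 working days.

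Below the table, with no split by causality: "All SAEs must be reported to the DCU (i.e., within 2 working days) after the investigator identifies the SAE". The opening of section 9.2.2 also makes investigators responsible for reporting SAEs immediately to the study designated physician.

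On who decides relatedness, the site investigator gives a view using Table 3 (section 9.1.3). For the study designated physician, section 9.2.2 says that "his causality assessment will take precedence over that of the site investigator". Section 5.5.1 makes the treatment codes available to that physician for regulatory reporting, and they "should be accessed only in the event that reporting necessitates unblinding".

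On the committee, section 5.5.1 says: "The Data and Safety Monitoring Committee (DSMC) will be able to unblind patients". Section 10.6 leaves meeting frequency to a charter and lets the chair or the study physician call an ad hoc meeting. Table 4 says DSMB and sections 5.5.1 and 10.6 say DSMC; I read them as the same body.

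**The concern.** The committee is the independent body that can look at deaths by arm while the trial runs. Under Table 4 it is the funder and the coordinating unit that hear of every death within days. The committee hears promptly only of those already attributed to the drug.

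Attribution is a weak filter for deaths in this disease. Hepatic death is both a natural outcome of alcoholic hepatitis and a conceivable form of drug harm, and the judgement is made one case at a time, normally blind. Table 3 adds to the difficulty. Definite, probable and possible each require a known or expected response pattern, and anything that fits none of the listed categories is not related. A new fatal toxicity with no established pattern in this population could, on a literal reading, fall on the slow route. Section 9.3 itself recognises, for expected SAEs, that harm may show only when the groups are compared in aggregate.

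At stake is the committee's chance to see deaths accumulate while patients are still being randomised or dosed. Deaths in follow-up count for this purpose too. Stopping rules and care for the individual patient are not in question.

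**Working it through.** **Following the table**

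| Recipient | Death judged related (SUSAR row) | Death judged unrelated (SAE row) |
|---|---|---|
| NIAAA | 2 working days | 2 working days |
| DCU (text of 9.2.2, all SAEs) | 2 working days | 2 working days |
| Study physician (text of 9.2.2, all SAEs) | immediate | immediate |
| DSMB | 2 working days | every 6 months |

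Of these four recipients, only the committee has a clock that depends on attribution. I looked for text that would override this in sections 5.5.1, 5.9, 8.5, 9.3 and 10.6. None requires earlier notice to the committee of a death judged unrelated.

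**Length of the scheduled wait**

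Inputs: the 6-month interval (Table 4); the assumption that deaths are spread evenly between reports, with no allowance for a data cut-off or report preparation.

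- 6 months = 365.25 / 2 = 182.6 days, the longest wait.
- Mean wait = 182.6 / 2 = 91.3 days.
- Share waiting more than 30 days = 1 − 30/182.6 = 0.836.
- Share waiting more than 90 days = 1 − 90/182.6 = 0.507.
- Share waiting longer than one 42-day treatment course = 1 − 42/182.6 = 0.770.
- Comparator: 2 working days is 2 to 4 calendar days when a weekend intervenes.

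**Illustration only: enrolment during the wait**

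At the planned pace (section 3.2.1: about 15 months; about 60 patients) accrual is 60/15 = 4 a month. The mean wait of 3 months then covers 3 × 4 = 12 randomisations and the longest covers 6 × 4 = 24, half of them to OCA. These counts describe the calendar; they do not measure harm.

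**Number of extra reports**

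The documents give no expected death rate for this trial. Assuming 180-day mortality of 3% to 20%, deaths are 60 × 0.03 = 1.8 to 60 × 0.20 = 12. For reference, the nearly 7% in-hospital mortality that section 1 cites for alcoholic hepatitis generally would give 60 × 0.07 = 4.2. These are upper bounds on the extra initial reports, because deaths judged related already go to the committee within 2 working days.

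**The case against.** The strongest reply is that the committee is not cut off. The study physician learns of SAEs immediately, holds the IND, carries primary responsibility for participant safety, and may convene the committee ad hoc. Section 9.3 foresees an aggregate comparison of expected SAEs against a concurrent or historical control. At the DCU, which has a Safety Officer, "the randomization codes and corresponding treatment assignment will be maintained by the TREAT DCU". Section 5.9 lets the consortium stop the trial and adds: "It is normal procedure to review the emerging clinical and safety data". The charter may already require prompt notice of deaths. Tiering by causality is also a recognisable choice: Amendment 3 revised Table 4 and shortened the SUSAR clock to the DSMB.

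All of this stands and lowers the weight of the point, but it does not close the gap. The physician's power to call a meeting is discretionary and lies with the person whose causality view decides the route. The chair's matching power cannot be used on a death the chair has not heard of. The aggregate comparison has no schedule, and its list of events does not include death. Neither the DCU's access to codes nor the right to terminate obliges anyone to tell the committee.

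A reader might also infer that section 8.5 does the routing, because it has each listed event, death included, adjudicated by the site "investigator as expected as part of the natural history of moderately severe AH, or unexpected". The documents do not support that. Section 8.5 sorts by expectedness; the Fatality row sorts by relatedness. A death classed as natural history but judged related still follows the SUSAR timeline. Nor does Table 3 bar a disease-compatible death from being called possible: that category allows for other ready explanations, provided timing and response pattern fit.

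Finally, a single arm-blind report may tell the chair little. That is true of one report; the benefit comes from seeing them accumulate.

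**Conclusion.** The point holds as a gap in the reporting schedule. A death judged unrelated has a scheduled wait of up to about 183 days before it reaches the committee, with a mean of about 91 days under even spacing, against 2 working days for the NIAAA and the DCU. Under the same assumption about 77% of such deaths would wait longer than a full treatment course. The look-up rests only on Table 4 and the text around it. What could remove the gap is the charter, which is not in the documents.

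Two stronger readings should be avoided. The plan does not prevent the committee from hearing sooner, since the study physician can bring a death to it at any time; it simply does not require this. And the 12 or 24 patients randomised during a wait at the planned pace are not patients exposed to avoidable harm, because nothing in the documents shows that one blinded death notice would pause enrolment. Sample size, type I error and the planned efficacy analysis are unaffected. This is a cheap safety improvement that should be made.

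**What to change.** In the Fatality row of Table 4, state that every death through Day 180, whatever its attribution, is sent to the DSMB chair within 2 working days. The notice can stay arm-blind; the chair can then use the ad hoc meeting power in section 10.6 and the committee's ability to unblind in section 5.5.1. Keep the related/unrelated split for the other recipients, and keep the 6-monthly summary. Leave non-fatal SAEs as they are: section 9.3 anticipates many of them in this population, and tiering those is reasonable. If the charter already requires prompt notice of all deaths, replace the new wording with a cross-reference to it.

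The cost is one table row and, under the mortality range assumed above, at most about 2 to 12 extra initial reports over the whole trial, plus any follow-up reports. Each uses a report that already has to be prepared on the 2-working-day clock for the NIAAA and the DCU.

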#### *9.2.2.1. Additional Principal Investigator Responsibilities for SAEs*

The safety data recorded in the CRF represent the official record of all AEs and SAEs reported in the trial. The investigator should comply with requests by the designated study physician to record the SAE on the patient's AE CRF and, if necessary, provide a copy of this CRF to the DCU. Other supporting documents such as radiology reports, hospital discharge summaries and autopsy reports should also be provided, when appropriate, in anonymized fashion. Additionally, upon request by the designated study physician, the investigator should provide input into the SAE narrative and provide timely information to ensure prompt follow up and closure of the SAE report.

The investigator and supporting personnel responsible for patient care should discuss with the designated study physician any need for supplemental investigations of SAE(s). The results of these additional assessments must be reported to the designated study physician.

### **9.3. SAEs THAT ARE ANTICIPATED TO OCCUR IN THE STUDY POPULATION (EXPECTED SAEs)**

Certain SAEs are anticipated to occur in this study population at some frequency independent of drug exposure. These expected SAEs have been identified as: variceal bleeding, ascites, spontaneous bacterial peritonitis, jaundice, hepatorenal syndrome, or hepatic encephalopathy. These expected SAEs as well as any related hospitalization will not be expeditiously reported as IND safety reports, but will be reported in the manner described above (9.2.2). However, if an aggregate analysis indicates that these events are occurring more frequently in the drug treatment group than in a concurrent or historical control group, the SAEs will be reported as an IND safety report (21 CFR 312.32(c)(1)(c)).

### **9.4. FOLLOW UP OF AEs**

All AEs, including clinically significant laboratory values or physical examination findings relative to pretreatment assessments, must be followed during the trial until

the AE resolves, is no longer of clinical concern, has stabilized or is otherwise explained, or the patient is lost to follow up.

AEs ongoing at the final visit that are deemed to be ‘possibly, probably, or definitely’ related or of other clinical significance must be followed for as long as necessary to adequately evaluate the safety of the patient or until the event stabilizes, resolves, or is no longer of clinical concern. If resolved, a resolution date for the AE should be documented on the CRF. The investigator must ensure that follow up includes any supplemental investigations indicated to elucidate the nature and/or causality of the AE. This may include additional laboratory tests or investigations, or consultation with other healthcare professionals, as considered clinically appropriate by the investigator.

## 10. STATISTICAL METHODS

### 10.1. ANALYSIS SETS

Primary end point: Analysis will be based on intention-to-treat principle. We will evaluate the main outcome, change in MELD score at day 42, in the framework of the repeated measurements analysis of covariance (ANCOVA) model. Specifically, MELD score at each follow-up visit will be used as the outcome variable. The main predictor is treatment group (GROUP). We will adjust for time (visit) and baseline MELD score and include the interaction between GROUP and visit. The interaction term allows evaluation of GROUP difference at each visit. The main comparison is the differences of MELD score change at day # 28 between two groups. A random intercept will be used to adjust for the correlation among the observations from the same subject. We will also evaluate the GROUP difference at 90 and 180 days in the framework of above repeated ANCOVA model.

SAEs during treatment: The primary analysis is to compare the proportion of patients having at least one SAE during the treatment period between the two groups using Chi-square tests. *SAE during follow-up* will be analyzed similarly. Other safety outcomes include AEs, discontinuations, pre-defined laboratory abnormalities, and predefined EKG abnormalities. Other continuous outcomes will be analyzed in a similar way to MELD score, binary outcomes will be analyzed in a similar way to SAE, and censored time-to-event outcomes will be analyzed using appropriate survival analysis tools (e.g., Kaplan-Meier plots, Cox models).

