### Planned Number of Investigational Sites

Four investigational trial sites at Indiana University in Indianapolis, Mayo Clinic in Rochester, Virginia Commonwealth University in Richmond, and Einstein Medical Center in Philadelphia

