## **5.4 RANDOMIZATION**

### **5.4.1 Method of Assigning Patients to Treatment Groups**

The trial will be conducted in a double-blind, placebo-controlled manner. Allocation to 1 of 2 treatment arms will occur on a 1:1 ratio within each sites with a block of size 4 based on a predefined randomization code generated by the TREAT data coordinating unit (DCU).

The investigator or designee will be required to register the patient on the OnCore system (TREAT's data management system) and will provide patient data to properly randomize and allocate the patient to treatment. A randomization number will be assigned and study medication dispensing information (e.g., bottle number(s)) will be provided.

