### **5.4.4 Randomization Numbers and Schedule**

Subjects will be randomized to one of two treatment groups with stratification by site and block of size 4. Random assignment will be generated by the coordinating unit and provided to the site pharmacist for randomized packing for maintenance of blinding.

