### 10.2. DETERMINATION OF SAMPLE SIZE

We examined the power of testing the difference in change of MELD score from baseline to day 28 with sample size of 30 in each group. Assuming a 10% drop out rate at day 28, we will have 27 subjects in each group. Using a two-sample t-test, we will have 80% power to detect any difference in effect size  $\geq 78\%$  of one standard deviation (smallest detectable effect size=0.78). The analysis using repeated-measurement ANCOVA will be more powerful than a two-sample t-test.

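### Randomisation is stratified by site but site is in neither primary analysis; adding it to the MELD model is a cheap, minor gain in precision if sites differ

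*Combined protocol and SAP*

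**What the plan says.** Section 5.4.4, repeated in the synopsis under Methodology, states: "Subjects will be randomized to one of two treatment groups with stratification by site and block of size 4". Section 5.4.1 agrees: "Allocation to 1 of 2 treatment arms will occur on a 1:1 ratio within each sites with a block of size 4".

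Section 10.1 then specifies the analyses. MELD at each follow-up visit is modelled on treatment group with the terms "We will adjust for time (visit) and baseline MELD score and include the interaction between GROUP and visit", and a random intercept handles repeated measures on the same patient. The main SAE analysis reads: "compare the proportion of patients having at least one SAE during the treatment period between the two groups using Chi-square tests". The same methods carry over to the rest: "Other continuous outcomes will be analyzed in a similar way to MELD score, binary outcomes will be analyzed in a similar way to SAE". No section brings site into the analysis of either primary objective.

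Section 10.2 sizes the trial without reference to site: "We examined the power of testing the difference in change of MELD score from baseline to day 28", using a two-sample t-test with 27 per arm after 10% dropout, 80% power and a smallest detectable effect of 0.78 SD. It adds: "The analysis using repeated-measurement ANCOVA will be more powerful than a two-sample t-test".

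**The concern.** Balancing the arms within each site removes between-site variation from the true sampling variance of the treatment difference. An analysis that ignores site still counts that variation as residual noise. If sites differ, the reported standard error then exceeds the real one, confidence intervals are wider than they need be, and the test rejects less often than its nominal 5% under the null. The design has paid for some precision that the analysis does not collect.

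Some site difference is plausible. Section 8.3 sends the blood tests that feed MELD to local laboratories (section 10.3.2 calls them central; the two need reconciling). Patients come from hospital and outpatient clinics, and SAE seriousness includes hospitalisation, which may depend on local practice. With 60 patients, what is at stake is modest precision, not the validity of the result.

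**Working it through.** **Inputs from the documents.** 30 randomised per arm; 10% dropout, so 27 per arm; 80% power; 0.78 SD of the change in MELD (10.2). Blocks of 4 within site (5.4). Four sites in the synopsis ("Four investigational trial sites at Indiana University in Indianapolis"), three in sections 4.1 and 8.3; both were tried.

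**Assumed, because the documents do not give them.** Two-sided 5% level; site's share of residual variance after baseline adjustment, 0 to 20%; site sizes 18/16/14/12; slope of follow-up on baseline MELD 0.5 with equal variances; within-patient correlation 0.6; SAE rates.

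**1. The plan's own figure.** Noncentral t with 52 df and noncentrality d × √(27/2). At d = 0.777, noncentrality is 2.855 and power is 80.0%; at d = 0.78 it is 80.3%. The stated 0.78 reproduces. A one-sided 5% level would give 0.686, so two-sided is the reading that fits.

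**2. Put the effect on the scale of the planned model.** The 0.78 is in SDs of the change score. With common SD σ and slope ρ = 0.5:
- change-score SD = σ√(2(1 − ρ)) = σ
- residual SD after baseline adjustment = σ√(1 − ρ²) = 0.866σ
- effect = 0.777 / 0.866 = 0.897 residual SD

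Power with 27 per arm is then 89.9% before site is considered.

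**3. Mechanism.** If site explains a share R² of residual variance and arms are balanced within site, the true variance of the difference is close to (2/n)(1 − R²), in units of residual variance. The analysis without site reports about (2/n). The standard error is too large by 1/√(1 − R²): 1.026 at 5%, 1.054 at 10%, 1.118 at 20%. Random dropout after allocation weakens the balance. In simulation the ratio of model SE to empirical SD was 1.03-1.05 at 10% and 1.07-1.10 at 20%.

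**4. Power for MELD.** Simulation of the random-intercept model: 60 randomised, 54 analysed, three visits, 8,000 trials per scenario, Monte Carlo SE of the gain 0.12-0.22 points. Power (%) without and with site:

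| Assumed site share | Random site effects | Gain | Site effects fixed at the share | Gain |
|---|---|---|---|---|
| 0% | 90.0, 89.6 | −0.4 | 89.8, 89.6 | −0.2 |
| 2.5% | 90.5, 90.8 | +0.3 | 90.2, 90.1 | −0.1 |
| 5% | 90.0, 90.4 | +0.4 | 90.3, 91.2 | +0.9 |
| 10% | 91.8, 93.1 | +1.3 | 90.1, 91.9 | +1.8 |
| 20% | 92.4, 95.0 | +2.6 | 91.3, 94.8 | +3.5 |

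The standard error with site is smaller by 1.7-2.4% at 5%, 3.6-5.0% at 10% and 7.8-10.6% at 20%. A simpler single-visit ANCOVA gives gains of about 0.5, 1.7 and 3.4 points at the same shares.

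**5. Type I error for MELD** (20,000 trials, fixed site effects), without and with site: 5.0 and 4.9% at 0%; 4.6 and 4.9% at 5%; 4.3 and 5.4% at 10%; 3.3 and 5.1% at 20%. Omitting site makes the test conservative, never liberal.

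**6. Sensitivity for MELD.** With fixed site effects, slope 0.3 gives gains of 1.1 points at 10% and 2.4 at 20%; slope 0.7 gives 2.2 and 4.2. Three sites of 20 give 1.3-2.2 at 10% and 2.7-3.3 at 20%. Sections 10.1 and 10.2 disagree on whether the main contrast is day 28 or day 42; under the assumed correlation structure the two behave alike here.

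**7. SAEs.** 60,000 trials per scenario, placebo-arm rate averaging 20%, four sites. Power (%) of chi-square, then Cochran-Mantel-Haenszel (CMH):

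| Placebo-arm rates across sites | Odds ratio 3 | Odds ratio 5 |
|---|---|---|
| 20% everywhere | 48.4, 48.2 | 83.1, 83.1 |
| 15-25% | 47.3, 47.5 | 82.3, 82.6 |
| 10-30% | 44.3, 46.1 | 79.2, 80.6 |

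The gain is about 0 to 1.8 points. Three sites of 20 at 10-30% give 42.9, 45.6 and 78.1, 80.0, a gain of up to about 2.6 points. At odds ratio 2 with four sites, both tests have about 20% power and differ by −0.2 to +1.0 points.

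**The case against.** The strongest reply is that nothing is broken. A conservative test is a legitimate choice, the sample size never relied on site, and on the change-score reading MELD power is already about 90%. Every site enrols within the same narrow MELD range and baseline MELD is a covariate, so a constant laboratory offset between sites would be partly absorbed. All of this stands, and it is why the point is minor.

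A reader might infer that the omission gives up several points of power. That needs a share near 20%, or 0.78 read as an SD of the residual after baseline adjustment, where the gain at 20% is 4.2 to 6.1 points. Section 10.2 states 0.78 for the change score with a t-test, and no section gives a between-site variance, so the documents support neither condition. A reader might also call the two outcomes co-primary; the documents list two primary objectives, do not use that term, and describe change in MELD as the main outcome.

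Two further objections stand in part. The simulations used one or three visits, whereas Table 1 schedules six after baseline, all available to the planned model; the direction carries over but the decimals should not be pressed. For SAEs, stratifying over small sites brings sparse strata for very little gain, and the odds ratios that give useful power are large: odds of 0.25 × 5 = 1.25 mean about 56% against 20%. That is enough to make the stratified test optional.

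**Conclusion.** The mismatch between design and analysis is real and clear from the text, and its consequence is a conditional loss of efficiency. The treatment estimate is not biased, type I error is at or below nominal without site, and the planned 80% power is met. Whether the recoverable gain in MELD power is negligible or reaches the 2.6 to 3.5 points found at a 20% share depends on a site share that the documents do not supply. The figures rest on that assumed share, the assumed slope and correlation, and 0.78 read as change-score SD. The SAE figures rest on assumed rates and odds ratios. This is a cheap improvement, not a correction that the trial's conclusions depend on.

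**What to change.** In section 10.1, add site as a fixed effect to the repeated-measures MELD model and to the other continuous outcomes analysed the same way. If very small sites are to be pooled, write the rule now and apply it to blinded enrolment counts before unblinding; choosing to add or pool sites after seeing results by arm would be data-driven.

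For SAEs, keep the chi-square test. A CMH test stratified by site, with a Mantel-Haenszel risk difference, may be reported alongside it.

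The cost is SAP wording and up to 3 degrees of freedom with four sites. If sites do not differ, it is about 0 to 0.6 points of MELD power and, where CMH is used, 0 to 0.4 points for SAEs. The number of sites (four in the synopsis, three in sections 4.1 and 8.3) should be reconciled as a separate document correction.
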